#### **Diagnostic and Laboratory Abnormalities**

- 22. Participants with the following toxicities at screening as defined by the enhanced Division of Microbiology and Infectious Disease (DMID) adult toxicity table (Draft November 2007) (Appendix 2) where applicable:
  - a. Platelets < 75,000/mm^3
  - b. Creatinine >1.5 times upper limit of normal (ULN)
  - c. eGFR ≤ 60 mL/min
  - d. Haemoglobin <8.0 g/dL
  - e. Serum potassium less than the lower limit of normal for the laboratory. This may be repeated once
  - f. AST:
    - ≥3.0 x ULN to be excluded
    - results between 1.5 x ULN and 3 x ULN must be discussed with and approved by the Sponsor Medical Monitor
  - g. ALT:
    - $\geq$  3.0 x ULN to be excluded
    - greater than ULN must be discussed with and approved by the Sponsor Medical Monitor
  - h. ALP:
    - $\geq$  3.0 x ULN to be excluded
    - 2.0 <3.0 x ULN must be discussed with and approved by the Sponsor Medical Monitor
  - i. Total bilirubin:
    - >1.5 x ULN to be excluded
    - Greater than ULN must be discussed with and approved by the Sponsor Medical Monitor
  - j. Direct bilirubin:
    - greater than 1x ULN to be excluded

k. Positive hepatitis B surface Ag, or hepatitis C antibody

All the inclusion and none of the exclusion criteria must be met. If no single variable/value is outside of the ranges of acceptability, but when multiple values are close to the limits and/or whenever the Investigator has reason to suspect that there might be a health problem (other than TB), enrolment should only be considered after discussing the case with the Sponsor Medical Monitor.

## 6.3 Restrictions

Concomitant medications should be kept to a minimum during the treatment period of the trial. However, if concomitant medications are necessary for the participant's welfare and are unlikely to interfere with the IMP, they may be given at the discretion of the Investigator. For any concomitant medications given as a treatment for a new condition or a worsening of an existing condition occurring after signing of the Informed Consent Form, the condition must be documented on the Adverse Event pages of the electronic Case Report Form (eCRF).

The prescribing information for all concomitant medication should be consulted and reviewed carefully. The determinations listed in the respective contraindicated, warning, and precaution sections must be respected to prevent any potentially serious and/or life-threatening drug interactions.

The following recommendations should be followed with regards to concomitant medication to avoid possible drug interaction with the IMP:

**Moxifloxacin**: The IMP should be taken either 4 hours before or 8 hours after taking the following products:

- An antacid, multivitamin, or other product that has magnesium, aluminium, iron, or zinc
- Sucralfate
- Didanosine

The following medicinal products are prohibited from the Screening visit and during the treatment period:

- Quinolone antimalarial (e.g., chloroquine and quinacrine). Participants who have malaria at screening are to be excluded. However, if a participant develops malaria during the trial, the Investigator is advised to consult the Malaria Treatment Guidance document regarding the interaction between moxifloxacin and bedaquiline with anti-malarial drugs. Investigators may also contact the Sponsor Medical Monitor for further guidance.
- Medicinal products used to treat pulmonary TB: including but not limited to gatifloxacin, amikacin, cycloserine, rifabutin, kanamycin, para-aminosalicylic acid, rifapentine, thioacetazone, capreomycin, other quinolones except moxifloxacin, thioamides, and metronidazole.

The following medicinal products should be avoided from Day 1 (Baseline visit) and during the treatment period as much as possible. Investigators may also contact the Sponsor Medical Monitor for further guidance.

- Any drug known to prolong QTc interval (including but not limited to amiodarone, bepridil, chloroquine, chlorpromazine, cisapride, clarithromycin, disopyramide dofetilide, domperidone, droperidol, erythromycin, halofantrine, haloperidol, ibutilide, levomethadyl, mesoridazine, methadone, pentamidine, pimozide, procainamide, quinidine, sotalol, sparfloxacin, thioridazine). The exception is moxifloxacin and Bedaquiline administered as part of the trial IMP, with ECG monitoring, to help ensure participant safety.
- to be (including but Any drug known hepatotoxic not limited to • acetaminophen/paracetamol, acetazolamide, allopurinol, amiodarone, amitriptyline, amoxicillin, amprenavir, atorvastatin, augmentin/co-amoxiclav, azathioprine, baclofen, bumetanide, captopril, carbamazepine, celecoxib, chlorpromazine, clindamycin, clopidogrel, co-trimoxazole, darunavir, delavirdine, diclofenac, doxycycline, enalapril, fluconazole, fluoxetine, fosamprenavir, furosemide, gliclazide, glimeperide, glipizide, ibuprofen, irbesartan, ketoconazole, lisinopril, loperamide, losartan, methotrexate, metolazone, mirtazepine, nitrofurantoin, omeprazole, other non-steroidal antiinflammatory drugs, paroxetine, phenobarbital, phenothiazines, phenytoin, pravastatin, probenecid, prochlorperazine, risperidone, rosuvastatin, sertraline, simeprevir, simvastatin, sodium valproate, sotalol, sulfasalazine, sumatriptan, tamsulosin, terbinafine, tetracycline, theophyllin/uniphyllin, tipranavir, tolazamide, tolbutamide, topiramate, trazodone, tricyclic antidepressants, trimethoprim, verapamil).

# Discontinuation from Treatment/Trial

The following may result in the discontinuation of trial treatment:

- Withdrawal of informed consent.
- Investigator considers that for safety reasons it is in the best interest of the participant that he be withdrawn, including a concern that the participant has symptomatic TB and/or bacteriological failure/relapse and requires a change in TB treatment.
- Adverse event resulting in death.
- Lost to follow-up.
- Termination of the trial by the sponsor.

A participant may withdrawal from the trial at any time at his/her request (withdrawal of consent) or may be withdrawn at any time at the discretion of the Investigator for safety, behavioral, compliance or administrative issues. When a participant withdrawals consent for the trial, no additional follow-up visits will be performed.

Participants who withdraw from the trial before 9 months maybe replaced and should be discussed with the Sponsor medical monitor.

All Participants withdrawal from trial treatment/received at least one dose of IMP will be requested to return for an early withdrawal visits and applicable safety Follow Up visits, as per flow chart (Section 1.1.1).

# 6.3.1 Early Withdrawal

In case of early withdrawal during the treatment or follow-up period, all efforts shall be made to complete the Early Withdrawal assessments. At the Early Withdrawal visit the following information will be collected and procedures performed:

- Two Spot sputum samples at least 30 minutes apart will be collected under the coaching and observation of the trial staff.
- Semen sampling collection: one pair of semen samples one week apart, each sample must be collected at least 2 days after abstinence from ejaculation.
- Laboratory safety sampling (including male reproductive hormone tests: LH, FSH, inhibin B and testosterone)
- Pharmacokinetic sampling (pre-dose within 2 hours prior to dosing)
- Single 12-lead ECG
- Vital signs
- Full physical examination, including weight
- IMP compliance check (if participant on IMP)
- Concomitant medications
- Adverse Events

# 6.3.2 Unscheduled Visits

Any visit which is conducted in addition to those required by the Synopsis Flow Chart and Procedures (Section 1.1.1), should be considered unscheduled regardless of the reason for the visit. The assessments which are undertaken as part of an Unscheduled visit should be as clinically indicated.

If the duration of treatment is extended due to dose interruptions/pauses, the last visit of the treatment period should also be pushed out to the date of the last dose. It is not necessary to have an unscheduled visit at the time that the last visit of treatment period would have been.

# 6.3.3 Lost-to-Follow-up

Every reasonable attempt must be made to minimise Lost-to-Follow-up (LTFU) participants. A minimum of three contact attempts (telephonic/home visit) will be made for participants who do not arrive for their scheduled trial visits. If these attempts are unsuccessful the participant will be considered LTFU. All attempts to contact the participant must be clearly documented in the participant's source documents.

# 6.3.4 Early Withdrawal due to TB

Ultimately it is the Investigator's decision whether a participant requires early withdrawal from the trial due to a concern that the participant has symptomatic worsening of TB and/or bacteriological failure/relapse.

Early withdrawal is usually not indicated for a single positive culture. Should a participant have a single positive culture result after being converted to culture negative, the Investigator is to evaluate whether the participant has signs and symptoms suggestive of active inadequately treated TB and whether it is in the participants best interest that he/she be withdrawn. Prior to early withdrawal of a participant due to TB, the Investigator must discuss the participant with the

Sponsor Medical Monitor, unless the Investigator cannot contact the Sponsor Medical Monitor and considers that early withdrawal must occur immediately due to immediate safety concerns with respect to the participant.

If the Investigator decides to withdraw a participant due to TB, additional sputum samples may need to be collected to ensure the participant's outcome status as determined in Section 1.1.1.

All early withdrawn participants who are confirmed sputum positive (two sequential sputum positive cultures) and/or have symptomatic TB will require further TB treatment. These participants will be referred to their applicable DR local community TB clinics for standard anti-tuberculosis chemotherapy according to local treatment guidelines.

The participant will be provided with a referral letter from the Investigator to take with them to their local treatment clinic and the referral letter, at a minimum, should include all treatment received by the participant and information about any suspected/confirmed adverse event/reaction related to any of the trial IMP's and or concomitant medications. A follow-up call should be made by the trial site staff to the clinic to ensure the participant attended their local treatment clinic.

# 6.4 Participant Progress Definitions

Status	Treatment	Follow-Up		
Screen Failure	Participants from whom informed consent is obtained and is documented in writing (i.e., participant signs an informed consent form) but who is not entered into the study			
Completed Treatment / Completed FU*	Participants who complete the full course of IMPParticipants who complete all follow-u visits			
Completed Treatment / Discontinued FU	Participants who complete the full course of IMP	Participants who do not complete all applicable follow-up visits, regardless of the reason (excluding LTFU)		
Completed Treatment / Lost to Follow-Up	Participants who complete the full course of IMP	Participants who are unable to be contacted on or before their final visit		
Discontinued Treatment / Completed FU	Participants who discontinue treatment prior to completion of the protocol-defined treatment course	Participants who complete all applicable follow-up visits		
Discontinued Treatment / Discontinued FU**	Participants who discontinue treatment prior to completion of the protocol-defined treatment course	Participants who do not complete all applicable follow-up visits, regardless of the reason (excluding LTFU)		
Lost to Follow-Up	Participants who are unable to be contacted on or before their final treatment visit and it cannot be confirmed whether treatment was completed			

Table 2: Participant	Progress	Definitions
-----------------------------	----------	-------------

\* Note that this includes treatment failures who complete all applicable follow-up visits

\*\* Early Withdrawal

# 6.5 Trial Stopping Rules

The Sponsor has the right to stop the trial or a specific trial site at any time, although this should only occur after consultation between the involved parties. Should this occur, the local and central Ethics Committee/Institutional Review Board (EC/IRB) and Regulatory Authorities will be informed.

Should a trial site be closed prematurely, all trial materials (except source documentation that must remain at the site) will be returned to the Sponsor or applicable vendor. The Investigator will retain all other documents until notification given by the Sponsor for destruction. Participants currently on trial IMP will receive an appropriate regimen and all participants will be referred to their applicable DR-TB NTP clinic.

For potential stopping rules regarding reproductive safety, refer to safety monitoring Section 9.4.

## 7 Treatment

## 7.1 IMP Administration

- Treatment will be administered orally once daily, to be taken with a meal approximately the same time each day with a glass of water (approximately 240 ml) for 26 weeks in the following dosing scheme:
  - Bedaquiline 200 mg once daily for 8 weeks then 100 mg once daily for 18 weeks, together with pretomanid 200 mg + moxifloxacin 400 mg + pyrazinamide 1500 mg once daily for 26 weeks (total treatment duration 6 months).

## 7.2 Participant Compliance

During treatment visits, the IMP will be administered by the Investigator(s)/designated site personnel and when possible, the check for IMP compliance via the hand-and-mouth procedure (both the hand and the mouth of the participant will be checked to ensure that the participant has swallowed the IMP). During the trial, sites will be responsible for ensuring participants are taking IMP correctly and are fully trained on how the IMP is to be taken, as well as to check the IMP cards for unused tablets in the containers at each visit during the treatment phase.

## 7.3 Treatment Modification(s)

The importance of adherence to the treatment schedule will be reinforced at each visit. Non-adherence should prompt the Investigator to identify and address the cause(s) (e.g. side effects).

A 'dose of IMP' is defined as the correct medication strength of bedaquiline + pretomanid + moxifloxacin + pyrazinamide as required to be taken for the day per protocol.

Participants that do not take:

- Up to 7 consecutive doses of IMP doses: restart IMP, no extension of IMP required.
- If more than 7 to ≤ 35 consecutive doses of IMP: restart IMP and extend the IMP treatment by the number of consecutive doses missed. In this scenario, missed doses between Baseline (Day 1) through week 8 inclusive i.e., bedaquiline dose of 200mg BDQ, will need to be caught up before the participant can start week 9 treatment visit. Similarly, missed doses between week 9 through week 26 inclusive, i.e., bedaquiline dose of 100mg BDQ, will require a make up for completion of treatment. The final treatment visit should be pushed

out to the date of last dose. It is not necessary to have an unscheduled visit at the time when the end of treatment visit would have been.

- If more than 35 consecutive doses of IMP, discontinue IMP and withdraw participant from the trial.
- If the participant misses a total (sum) of 56 cumulative missed doses, discontinue the IMP and withdraw the participant from the trial.

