# **Trial Design Rationale**

The primary purpose of this Male Reproductive Safety – "BPaMZ/SEM"- clinical study is to generate data to evaluate the potential effect of once daily 200mg Pretomanid on human testicular function whilst being dosed for 6 months in patients with Drug Resistant (DR-TB) Pulmonary Tuberculosis. The 6 months dosing period covers current use of pretomanid is an approved antimicrobial regimen for the treatment of TB. (Pretomanid in combination regimen with Bedaquiline and Linezolid (BPaL) for people with XDR-TB or treatment-intolerant/non-responsive MDR-TB). It is not feasible to evaluate the potential testicular toxicity of once daily 200mg Pretomanid in this BPaL regime, as Linezolid has shown toxicity on testicular function in non-clinical studies. Therefore, the study will be conducted using the antimicrobial regimen consisting of Bedaguiline (B) plus Pretomanid (Pa) plus Moxifloxacin (M) and Pyrazinamide (Z) (BPaMZ) for 6 months in DR-TB patients. Participants will also be followed up to 18 weeks post dose to evaluate and ensure coverage of potential recovery of semen parameters which encompasses one and one-half cycles (cycle length is around 75 days) of the seminiferous epithelium. This also includes epididymal transit time (since we are sampling and evaluating semen), which adds another  $\sim 10$  days. Thus, in days 75 + 37.5 + 10 = 122.5 days or 17.5 weeks, therefore 18 weeks should be sufficient for follow-up period.

The safety of pretomanid has been tested in 10 single- and multi-dose Phase I studies with healthy adult male and female participants, receiving single oral doses of pretomanid ranging from 50 to 1500 mg and multiple oral doses ranging from 200 to 1000 mg/day given for up to eight days. Pretomanid has also been studied in combination regimens in patients for up to 9 months in Phase 2 and 3 studies. For this study adult male DR-TB patients who can complete the trial will be required.

For assessment of the male reproductive safety profile the following parameters will be evaluated in adult male participants with Drug Resistant (DR-TB) Pulmonary Tuberculosis.

For assessment of the male reproductive safety profile the following parameters will be evaluated.

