7.3. Adequate treatment

The definition of adequate treatment sets a limit for the amount of treatment missed. Participants not taking the adequate amount of treatment by this definition will be excluded from the per protocol analyses (PP and TB-PP).

To meet the definition of adequate treatment participants must have taken at least 146 doses (80%) of their allocated 182 day (26 weeks) treatment regimen within 238 days of starting therapy (i.e. 26 weeks plus an allowable 56 day halt (including a maximum of 35 consecutive days) as per the protocol).

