8.1.2. The per-protocol (PP) population

The primary and secondary semen analyses will also be conducted on the PP population, defined as all participants who were enrolled and started treatment, excluding:

1. Participants not meeting the definition of having received an adequate amount of treatment.

2. Participants classified as major protocol deviations for analysis (see §7.4).

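### The semen per-protocol rule counts doses over the whole course, so it can admit a man who was off drug for 36 of the 85 days before his Week 26 sample

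*Protocol*

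**What the plan says.** Protocol Section 7.3 sorts dosing gaps by length. For short ones: "Up to 7 consecutive doses of IMP doses: restart IMP, no extension of IMP required". For runs of more than 7 and up to 35, the site is to "restart IMP and extend the IMP treatment by the number of consecutive doses missed". Beyond that: "If more than 35 consecutive doses of IMP, discontinue IMP and withdraw participant from the trial". Withdrawal also follows at 56 missed doses in total. When treatment is extended, Protocol Section 1.1.1 (Unscheduled Visits) moves the end-of-treatment visit and all later visits accordingly.

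SAP Section 7.3 defines adequate treatment: "participants must have taken at least 146 doses (80%) of their allocated 182 day (26 weeks) treatment regimen within 238 days". The 238 days are 26 weeks plus a permitted halt of 56 days, at most 35 of them consecutive. One definition serves both the semen and the TB per-protocol sets. SAP Section 8.1.2 removes from the semen set "Participants not meeting the definition of having received an adequate amount of treatment", together with major protocol deviations. The ITT set (SAP Section 8.1.1) needs only one dose. None of these rules says when in the course the doses must fall.

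The time scale is in the Trial Design Rationale (Protocol Section 2.1): "cycle length is around 75 days". On transit it says "This also includes epididymal transit time (since we are sampling and evaluating semen), which adds another" 10 days or so, and it sums one and a half cycles plus transit as "in days 75 + 37.5 + 10 = 122.5 days or 17.5 weeks" to justify the recovery follow-up.

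**The concern.** The trial is meant to rule out a severe effect on testicular function, and a semen sample reports on sperm formed over a limited recent period. The per-protocol set is the only planned semen population with an exposure requirement beyond one dose. A whole-course dose count is a natural rule for a TB cure outcome. It does not ensure that a man was on pretomanid while the sperm in his Week 26 sample were being formed.

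If some men were largely off drug in that period, any drug effect would tend to look smaller. The per-protocol summary could then be read as confirmation in well-exposed men when it is not. With 20 evaluable men, each man is 1/20 = 5 percentage points in the SAP's proportions with a 50% change in count.

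**Working it through.** **The plan's own figures.** 0.80 × 182 = 145.6, rounded up to 146 doses. 182 + 56 = 238 days. 75 + 37.5 + 10 = 122.5 days, and 122.5 / 7 = 17.5 weeks. All reproduce.

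**Relevant window.** One cycle plus transit is 75 + 10 = 85 days. The protocol does not print this sum; it is derived from the two figures in the Trial Design Rationale. The printed 122.5 days serves as a second window.

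**Schedules tested against the rules.** Each was checked for a run above 35, for 56 or more missed doses, and for at least 146 doses within 238 days. The sample is taken on the day of the last dose.

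| Schedule | Pattern (days) | Length | Doses taken | Missed | Off drug in last 85 days |
|---|---|---|---|---|---|
| Short gaps, not made up | 97 on; five rounds of 7 off and 8 on; 1 off; 9 on | 182 | 97 + 40 + 9 = 146 | 36 | 36/85 = 42% |
| One long gap, made up | 140 on; 35 off; 42 on | 217 | 182 | 35 | 35/85 = 41% |
| Two gaps, made up | 152 on; 35 off; 15 on; 20 off; 15 on | 237 | 182 | 55 | 55/85 = 65% |

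None of the three men is withdrawn, and all three are adequately treated under SAP Section 7.3. Their dosed days in the window are 49, 50 and 30 of 85. Over 122.5 days the shares off drug are 36/122.5 = 29%, 35/122.5 = 29% and 55/122.5 = 45%. The third schedule is a corner case: 55 missed doses against a limit of 56, and Day 237 against 238.

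**Does the sample stay in Week 26?** The short-gap course ends on Day 182, so the question does not arise. The made-up courses end on Day 182 + 35 = 217 (Week 31) and Day 182 + 55 = 237 (about Week 34). Protocol Section 1.1.1 moves the visit with the last dose. SAP Section 7.5 works from visit dates, defines the treatment period as 26 weeks from the start of therapy, and files scheduled visits outside their windows (±7 or ±14 days) as separate visits. SAP Section 7.6 imputes nothing. SAP Section 4 times the endpoint in weeks of therapy, which favours keeping the postponed sample, but the SAP does not settle it.

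**Would planned output show it?** SAP Section 9.3 plots the mean trough over Weeks 2 to 26 against the percentage change in count. In an unextended course the 85-day window opens after Day 182 − 85 = 97, about Week 14. Four of the seven scheduled troughs (Weeks 2, 4, 8, 12) come before it. The three inside it (Weeks 16, 22, 26) are 6 and 4 weeks apart, so runs of up to 7 missed doses can fall between them. No planned output counts doses in the window.

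**The case against.** **Reversibility.** A reader might infer that a fall in count shrinks in proportion to the days off drug, so that a large fall would slip under the SAP's 50% criterion. The documents do not support that. Protocol Section 2.1 (Background) reports that testicular effects in rats were partly and very slowly reversible after 7 days of dosing, and not reversible after 14. The protocol allows 122.5 days for recovery in men, and the made-up schedules above follow 140 or 152 uninterrupted doses. An established effect might dilute little. This stands, and it removes any claim about size.

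**Postponed samples.** A reader might infer that men with long made-up gaps count fully in the Week 26 summaries. That holds only if SAP Section 7.5 is read so as to keep a Day 217 or Day 237 sample. The short-gap case does not depend on it. Protocol Section 7.3 does say, in a line against giving make-up doses as monotherapy, that all missed doses are completed within the regimen; but its bullet on short gaps is explicit that no extension follows.

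**Existing pharmacokinetic output.** It would be too strong to say that nothing planned bears on exposure. SAP Section 9.3 summarises concentrations by visit and by 50% change in count, and plots troughs against the Week 26 change. These outputs help, but they are sparse or averaged over the whole course.

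**Frequency.** The documents give no rate of gaps. Even on the unsupported proportional assumption, the mean effect in 20 men shrinks by (k/20) × (days off/85) for k affected men: 2.1% to 3.2% for one man and 8.2% to 12.9% for four, with 35 to 55 days off. This is an illustration, not an estimate.

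**Selection.** The synopsis says the regimen may be paused for toxicity. Restricting a summary to men without late gaps could drop the men most sensitive to the drug, which also leans towards no harm. This stands, and it rules out replacing the present per-protocol set.

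**Role of the analysis.** All analyses are descriptive and the semen analyses are run first on ITT, so no test or margin is distorted. This also stands.

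**Conclusion.** The point holds in a limited form. The semen per-protocol rule has no condition on timing, and a man can satisfy it with 36 of the 85 days before his Week 26 sample off drug. With made-up gaps the figure is 35 to 55 of 85, provided the postponed sample is kept as Week 26. The direction is towards under-detecting an effect; the size cannot be stated.

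This rests on an 85-day window derived from the protocol's approximate figures and on schedules that the rules permit but whose frequency is unknown. A reader might go further and conclude that the primary result is biased by a known amount, or that the per-protocol set must be redefined. The documents support neither. What is missing is a view of exposure in the relevant period, and that is a cheap improvement to the SAP.

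**What to change.** Keep the ITT and current per-protocol semen summaries, and keep the 146-dose rule for TB-PP. Add to the SAP:

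1. For each man, the number of doses taken in the 85 days before the first sample of the Week 26-27 pair, and over 122.5 days (rounded to whole days), listed beside his Week 26 change in total sperm count, with the reason for any gap.
2. A pre-specified supportive summary of the primary outcome in men with at least 80% of doses in the 85-day window: 0.80 × 85 = 68. This reuses the SAP's own percentage. The three schedules above (49, 50 and 30 doses) would fall outside it. A fully adherent man sampled 14 days after his last dose would stay in, with 85 − 14 = 71.
3. A statement of whether semen samples from postponed end-of-treatment visits count as Week 26, reconciling Protocol Section 1.1.1 with SAP Section 7.5.
4. A reconciliation of the protocol's withdrawal at 56 missed doses with the SAP's permitted halt of 56 days. Which is right is for the sponsor to settle; no change to any dosing or withdrawal rule is proposed here.

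The cost is SAP wording, one derived variable, one listing and one summary. Dated missed doses are already needed to apply the limits on consecutive doses in Protocol Section 7.3 and SAP Section 7.3. Protocol Section 7.2 describes only supervised doses and tablet checks at visits, so the team should confirm that the dates are captured. The supportive set will be smaller and may leave out men who paused for toxicity, which is why it sits beside the per-protocol set and does not replace it.
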